**Comments.** We decided not to include any education or intervention directly targeting on smoking relapse. This will allow us to test the independent effect of breastfeeding promotion on smoking relapse.

**3.1.7 Follow-up.** To evaluate sustainability of the effects of breastfeeding promotion on smoking relapse, we will follow participants and infants in 9 months postpartum (i.e., 3 months after breastfeeding intervention ends).

**3.1.8 Outcome measures.** The key outcome measures include timing of postpartum smoking relapse (primary) and breastfeeding duration (secondary) derived from data repeatedly collected throughout the study (**Table 1**). Outcomes will be assessed by graduate research assistants who are blinded to group assignments.

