*Maternal negative affect.* Maternal negative affect will be measured at enrollment and all postpartum visits using the Positive and Negative Affect Schedule (PANAS). The 10 items on negative affect include being distressed, upset, guilty, ashamed, hostile, irritable, nervous, jittery, scared, and afraid. Participants will rate their experience of each particular emotion in the past few weeks. With this time frame, its Cronbach's alpha was 0.87 and test-retest reliability was 0.48. In addition, we will measure maternal anxiety with the State-Trait Anxiety Inventory and postpartum depression with the Edinburgh Postnatal Depression Scale.

**3.1.10 Covariates.** We consider partner smoking, maternal secondhand smoke exposure, education, household income, health motivation, perceived social support, as covariates. They may confound our results and will be controlled in data analysis if not comparable between intervention and control groups.

**3.1.11 Economic costs.** We will collect information on intervention (not research and development) costs such as personnel, recruitment, materials, compensation, incentives, and transportation. We will include outcome costs for formula, medical care of NICU stay and sick child visits, and parental absenteeism for infant illness.

**3.1.12 Statistical Analysis.** *Specific Aim 1 (Breastfeeding promotion and postpartum smoking relapse).* The timing of postpartum smoking relapse (outcome) will be analyzed with Cox regression model by including group assignment (intervention vs control), smoking status (1=smoking, 0=non-smoking), the observed time, and significant covariates. The proportional hazard ratio of postpartum smoking relapse between two groups will be calculated. We will estimate Kaplan-Meier survival curves to visually compare smoking trajectories. Intent-to-treat analysis will be used with all randomized participants being included in their originally assigned groups. Dropouts, losses to follow-up, fetal deaths, and miscarriages will be coded as missing data on smoking status. If missing data on smoking status is more than 20%, we will run pattern mixture models and sensitivity analyses. A supplemental analysis will be run to examine *prenatal* smoking relapse during pregnancy.

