*Specific Aim 2 (Mediation analyses on mechanisms).* We will use dynamic path analysis to examine the mechanisms through which breastfeeding reduces smoking relapse. The dynamic path analysis includes simultaneous fitting of the Aalen additive hazards model (the R package 'timereg') and ordinary path analysis (PROC TCALIS in SAS). It fits our survival data with internal time-dependent mediators (e.g., oxytocin or prolactin) and a counting process as the outcome (i.e., smoking relapse). Hormonal baseline level and response to infant feeding (oxytocin or prolactin) will be included into the model as independent mediators. We will estimate the direct, indirect (through one or multiple mediators), and total effects of breastfeeding on smoking relapse (**Figure 1**). The PI has sufficient experience in mediation analysis.

**3.1.13 Sample size.** According to the literature, we estimate 45% rate of smoking relapse by 6 months postpartum in the control group. Assuming 45% protection effect of breastfeeding against postpartum smoking relapse, we estimate 25% (45%\*[1-45%]) rate of smoking relapse by 6 months postpartum in the intervention group. The corresponding sample size is 98 per group with type 1 error  $\alpha$  of 0.05 and power  $1-\beta$  of 0.8 to detect significant difference in smoking relapse between two groups in the larger R01 project. If 9-month postpartum smoking relapse rates (70% control vs 39% intervention) are used, the corresponding sample size is 46 per group. Therefore, 30 participants per group for this pilot study should provide sufficient sample size to test feasibility and efficacy as well as provide preliminary data regarding mediators and cost-effectiveness.

**3.2 Potential Problems & Alternative Strategies.** A potential challenge for the proposed project is to recruit a sufficient number of pregnant ex-smokers. If significant delay is observed, we will expand recruitment areas, use direct mailing, and advertise in local media. Another potential problem is attrition during intervention and follow-up periods. We expect 20% attrition rate due to dropouts, losses to follow-up, miscarriages, and fetal deaths. If we lose contact, we will reach out to the 3 people that have close relationship with the participant indicated at enrollment. We will recruit more participants to ensure sufficient statistical power if attrition is high.

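### Two different, unreconciled, data-driven rules choose the covariates of the primary Cox model, so the primary hazard ratio is not one fixed analysis

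*Combined protocol and SAP*

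**What the plan says.** Timing of postpartum relapse is the primary outcome (3.1.8). For Specific Aim 1, section 3.1.12 plans a Cox regression with group, "smoking status (1=smoking, 0=non-smoking), the observed time, and significant covariates". The effect measure follows: "The proportional hazard ratio of postpartum smoking relapse between two groups will be calculated".

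Section 3.1.10 supplies the candidates: "We consider partner smoking, maternal secondhand smoke exposure, education, household income, health motivation", and "perceived social support". That makes six. It then gives its own condition for using them: "They may confound our results and will be controlled in data analysis if not comparable between intervention and control groups".

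The plan does not define *significant* (associated with relapse, or with group; in which model; at what level). It does not define *comparable* either. It does not say which section governs the primary model, and it does not name an unadjusted hazard ratio as primary.

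**The concern.** The two sections describe different selection steps. One, on its natural reading, keeps a covariate for its association with relapse. The other keeps it for a chance difference between randomised arms. Each can be applied only after trial data have been examined, and the first may need outcome data. With six candidates there are 2^6 = 64 possible covariate sets, counting the empty one.

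Three things are at stake:
- Selection on the outcome can push type I error above 5% in a small trial.
- Selection on imbalance ignores prognostic strength, which is what makes adjustment useful in a randomised comparison, so it can waste power.
- A Cox hazard ratio is not collapsible. The quantity being estimated changes with the covariates included.

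Section 3.1.13 says that 30 per group is enough to test efficacy, and section 3.4 says that the results will support a larger grant application. The primary estimate should therefore be one defined analysis.

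**Working it through.** **Plan's own figures.** In 3.1.13, "we estimate 45% rate of smoking relapse by 6 months postpartum in the control group", against 25% under intervention; the 9-month rates are 70% and 39%. The two-proportion formula with pooled variance, two-sided 5%, 80% power, is n = [1.960·√(2p̄(1−p̄)) + 0.842·√(p₁(1−p₁)+p₂(1−p₂))]² / (p₁−p₂)². With d = p₁−p₂, the continuity correction is n′ = (n/4)·[1+√(1+4/(n·d))]².
- 6 months: n = 88.1, n′ = 97.8, so 98 per group, as stated.
- 9 months: n = 39.3, n′ = 45.5, so 46 per group, as stated.

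These figures are unadjusted, so the covariate rule does not alter them.

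**Information at 30 per arm.** The 9-month rates give 30×0.70 + 30×0.39 = 32.7 events before dropout, and a hazard ratio of ln(0.61)/ln(0.30) = 0.41. The 6-month rates give 30×0.45 + 30×0.25 = 21 events. Group plus six covariates is seven parameters: 32.7/7 = 4.7 or 21/7 = 3.0 events per parameter.

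**How often chance imbalance triggers adjustment.** For six independent covariates tested at 0.05, the chance that at least one differs is 1 − 0.95⁶ = 26%. At 0.10 it is 1 − 0.90⁶ = 47%.

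**Simulation 1: equal strengths.** Inputs from the plan: 30 per arm, 70% control relapse at 9 months (before covariate effects), 20% dropout. Assumed: exponential times, six independent covariates (two of them two-level), all with log hazard ratio 0, 0.2 or 0.4 per SD. There were 3,000 trials per setting, and 5,000 for the unadjusted and two-covariate rows. Monte Carlo SE is about 0.4 points for error and 0.9 for power.

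| Model | Type I error %, strength 0 / 0.2 / 0.4 | Power % at HR 0.41 |
|---|---|---|
| Imbalance rule (p<0.05) | 4.5 / 4.2 / 3.9 | 63 / 59 / 44 |
| Significance, one covariate at a time | 4.4 / 5.0 / 6.0 | 63 / 58 / 50 |
| Significance in full model, then refit | 5.5 / 6.7 / 9.7 | 65 / 65 / 63 |
| Fixed, unadjusted | 5.0 / 5.1 / 5.1 | 66 / 60 / 45 |
| Fixed, two covariates | 5.4 / 5.7 / 5.7 | 65 / 61 / 51 |
| Fixed, all six | 6.9 / 6.3 / 7.1 | 63 / 65 / 64 |

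The imbalance rule and one-at-a-time significance chose different covariate sets in 43–46%, 72–79% and 95–98% of trials at the three strengths. Taking the smallest p over the unadjusted model, the imbalance rule, both significance rules and the union of imbalanced and singly significant covariates gave error of 6.1 / 8.2 / 13.3%.

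**Simulation 2: unequal strengths.** Control hazards follow the plan's rates: −ln(0.55)/6 = 0.0996 per month to month 6, then [ln(0.55)−ln(0.30)]/3 = 0.202 per month. Size and dropout are as before, with 2,500 trials per setting. Assumed strengths: (a) two covariates at 0.6 and four at 0.1; (b) all six at 0.3. Imbalance is a t-test p<0.05. Significance is a Wald p<0.05 in an arm-adjusted model. Ranges cover repeat runs.

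| Quantity | (a) | (b) |
|---|---|---|
| Error, significance rule | 6.9–7.4% | 8.3–9.1% |
| Error, either rule may be used | 9.0% | 9.7% |
| Power, imbalance rule | 46–48% | 52–53% |
| Power, two fixed covariates (in (a), the two strong ones) | 62–64% | 55–56% |
| Opposite verdicts at p<0.05, HR 0.41 | 22–23% | 15–17% |

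Two fixed covariates gave 5.7–6.0% error. With HR 0.41, opposite verdicts fell to 4.5–4.8% at strength 0 and 10.4% at 0.2; with no effect they were 1.5–6.8%. If the two fixed covariates in (a) are weak ones, the gain disappears: 46.5% power against 46.1% for the imbalance rule. Forcing in all six gave 6.6–7.9% error.

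**The case against.** The strongest reply is that the rules need not contradict each other. *Significant* could mean significantly different between arms, which would make 3.1.12 a shorthand for 3.1.10, or the rules could be applied in sequence. A reader might infer a flat contradiction. The documents do not support that; they support only that the rules differ as written and are not reconciled. The candidate list is also named in advance, so only selection from it is open.

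A reader might also infer that the plan inflates type I error as a matter of course. It does not. The imbalance rule is slightly conservative. One-at-a-time significance selection stayed at 4.4–6.0% in simulation 1. Part of the excess in simulation 2 is small-sample Wald error, because a fully fixed six-covariate model also exceeds 5%. The 15-point power loss needs a comparator in which the two strong covariates were correctly guessed. Against a fixed unadjusted model the imbalance rule loses only about 0 to 3 points.

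A third inference, that the analyst would choose the favourable model, has no basis: the documents do not describe the analyst's access to results.

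The simulations assume independent covariates. Partner smoking with secondhand exposure, and education with income, are plausibly correlated, and this was not tested. Finally, this is a pilot, and 30 per arm is below the plan's own 46 and 98 under any covariate rule. That reduces the consequence but does not remove it, since 3.1.13 claims a test of efficacy.

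What stands: neither rule has a criterion, and nothing says which one produces the primary hazard ratio.

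**Conclusion.** The concern holds in this limited form and should be fixed. The primary hazard ratio is not one fixed analysis, whatever the covariate strengths turn out to be. The numerical harm is conditional on strengths that the documents do not give:
- **Selection by significance with the outcome:** type I error of about 4 to 9%, reaching 9.7% when all six covariates are at 0.4 and selection uses the full model; about 10% if either rule may be used.
- **Selection by imbalance:** no inflation; power 0 to about 15 points below a model with two fixed covariates, with the large loss only if strong covariates are named correctly beforehand.
- **Disagreement between the rules at p<0.05:** about 5 to 23% of trials at a hazard ratio of 0.41.

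If the covariates are not prognostic, either rule applied alone does little damage. These figures rest on 30 randomised per arm with 20% dropout. Section 3.1.2 mentions recruiting 72 to allow for attrition; if more than 60 are randomised, the event counts rise somewhat.

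**What to change.** In 3.1.12, remove selection by significance. In 3.1.10, remove the imbalance trigger for Aim 1. Put in their place, before any by-arm or outcome data are seen, wording such as: *The primary analysis is a Cox model with group and [one or two named baseline covariates], entered whatever their balance or p-value. The unadjusted hazard ratio is reported beside it. Any other adjustment is a sensitivity analysis.*

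Choose the covariates for expected prognostic value. Partner smoking is one candidate: it is on the 3.1.10 list and is collected at the pre-test visit (3.1.4). An unadjusted primary model is an acceptable alternative and closes the gap equally well. Do not force in all six: with about 33 or fewer expected events under the planned effect, error was about 6 to 8%.

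The timeline in 3.3 shows data analysis from month 10, while recruitment is still running, so the wording should be settled before then. The cost is two sentences and no new data. The small downside is little or no power gain if the named covariates prove weak.

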### **3. Approach**

**3.1 Research Design.** **3.1.1 Overview.** This is a randomized controlled trial to prevent postpartum smoking relapse by breastfeeding promotion. The intervention group (N=30) will receive multicomponent breastfeeding intervention from late pregnancy to 6 months postpartum, while the usual care control group (N=30) will only receive minimum breastfeeding education. The key outcome is the timing of postpartum smoking relapse.

**3.1.2 Recruitment.** We will recruit 60 pregnant ex-smokers from Erie County and Niagara County, NY. Recruitment flyers will be distributed around the communities (e.g., churches, bus/subway stops, laundromats, grocery stores, thrift stores, community centers) and organizations providing basic services (e.g., social services, WIC, job training) to low income pregnant women. Recruitment flyers will also be displayed in 4 large city OB/GYN clinics. Health professionals at these clinics will pass our recruitment materials to ex-smoking patients. We will also send an invitation letter to potentially eligible pregnant women in these clinics. The PI has successful experience in recruiting 50 pregnant smokers for his NIH funded study on smoking cessation during pregnancy over 6 months from 2 obstetric clinics (see **Letters of Support** from clinics). Social media such as Facebook will also be used. Assuming a rate of 23% maternal smoking at conception and 54% smoking cessation rate during pregnancy, we estimate 1,490 out of about 12,000 newborns will be born to mothers who quit smoking during pregnancy within 1 year in the two counties. We assume 60% of these mothers (N=894) will be exposed to recruitment materials, and then 30% (N=268) are interested in this project. Therefore, it is feasible to recruit 72 (60 + 20% attrition) eligible participants within 1 year.

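### The 9-month follow-up is there to assess sustainability, but the single planned hazard ratio cannot tell a lasting effect from one that stops or reverses after 6 months

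*Combined protocol and SAP*

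**What the plan says.** Section 3.1.1 describes a "multicomponent breastfeeding intervention from late pregnancy to 6 months postpartum" and states that "The key outcome is the timing of postpartum smoking relapse". Section 3.1.7 explains why women are followed beyond that period: "To evaluate sustainability of the effects of breastfeeding promotion on smoking relapse, we will follow participants and infants in 9 months postpartum", which it notes is 3 months after the intervention ends.

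The Aim 1 analysis in section 3.1.12 is a Cox model containing group, smoking status, "the observed time, and significant covariates". From it, "The proportional hazard ratio of postpartum smoking relapse between two groups will be calculated". Kaplan-Meier curves will be estimated so that the arms can be compared by eye. The section plans no group-by-time term, no separate estimates before and after 6 months, and no between-arm difference with a confidence interval at either time. It does not state the time horizon of the Cox model; months 0-9 is my reading, because Table 1 collects smoking status up to M9.

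The Aalen additive model under Aim 2 allows effects to change over time, but it serves the mediation analysis of breastfeeding and not the randomised comparison.

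Section 3.1.13 works with relapse at fixed times: 45% against 25% at 6 months, and then "If 9-month postpartum smoking relapse rates (70% control vs 39% intervention) are used, the corresponding sample size is 46 per group".

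**The concern.** Sustainability is a question about what happens after month 6. A hazard ratio averaged over months 0-9 mixes the period in which counselling and incentives are running with the period after they stop. Under the plan's own rates, (45 + 25)/(70 + 39) = 64% of relapses by 9 months occur in the first 6 months, so the average leans towards the intervention period.

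An overall HR below 1 can therefore arise from a lasting effect, from an effect that ended at 6 months, or from one that later reversed. The trial is meant to inform a larger application with a longer intervention and longer follow-up (section 3.4). A reader of the pilot's result will want to know which pattern occurred, and the planned estimate does not say.

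**Working it through.** **The plan's figures.** The two sample sizes in section 3.1.13 reproduce as a two-sided comparison of proportions at alpha 0.05 and power 0.80, with continuity correction: 98 per group for 45% vs 25%, and 46 per group for 70% vs 39%. Without the correction they are 89 and 40. The rates can be taken as the plan's working assumptions.

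**Inputs from section 3.1.13.** Control relapse 45% at 6 months and 70% at 9 months; intervention relapse 25% at 6 months; 30 per arm. **My assumptions.** Constant hazards within months 0-6 and within months 6-9, no censoring before 9 months, and a 6-9 month HR that is varied.

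**Implied hazards.**
- Control, months 0-6: -ln(0.55)/6 = 0.100 per month.
- Control, months 6-9: ln(0.55/0.30)/3 = 0.202 per month.
- HR, months 0-6: ln(0.75)/ln(0.55) = 0.48.

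**Intervention relapse at 9 months** for a 6-9 month HR of h is 1 - 0.75 × (0.30/0.55)^h. With h = 1.0 this is 1 - 0.75 × 0.545 = 59%. The arms meet at 70% when h = ln(0.75/0.30)/ln(0.55/0.30) = 0.916/0.606 = 1.51.

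**Overall Cox HR.** With equal arms, the large-sample value is the HR that solves the partial-likelihood score equation: the sum over time of [f_I(1 - p) - f_C p] = 0, where p = HR × S_I/(HR × S_I + S_C), S is the proportion still relapse-free and f the relapse density in each arm.

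| Assumed 6-9 month HR | 9-month relapse, intervention vs control | Difference at 6 months | Difference at 9 months | Overall 0-9 month HR |
|---|---|---|---|---|
| 0.48 (effect continues) | 44% vs 70% | 20 points | 26 points | 0.48 |
| 1.00 (effect stops) | 59% vs 70% | 20 points | 11 points | 0.68 |
| 1.25 | 65% vs 70% | 20 points | 5 points | 0.77 |
| 1.51 (full catch-up) | 70% vs 70% | 20 points | 0 points | 0.85 |
| 2.00 | 78% vs 70% | 20 points | -8 points | 1.01 |

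The overall HR reaches 1 only at a 6-9 month HR of about 1.98, when 9-month relapse is already higher on intervention (77% vs 70%). With 20% independent dropout spread over 9 months, 0.68 becomes 0.66 and 0.85 becomes 0.83.

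**The same HR from a lasting effect.** A constant HR of 0.68 gives intervention relapse of 1 - 0.55^0.68 = 33% at 6 months and 1 - 0.30^0.68 = 56% at 9 months, so differences of 12 and 14 points. An effect that stops gives 20 and 11 points. Both produce an overall HR of about 0.68; only the pair of differences separates them.

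**At 30 per arm** (8,000 simulated trials, no dropout). If the effect stops, the overall HR is below 1 in 89% of trials and significantly protective in 22%. At a 6-9 month HR of 1.5, the figures are 71% and 7.5%.

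**Precision of the additions.**
- 9-month difference at 70% vs 39%: SE = √(0.70 × 0.30/30 + 0.39 × 0.61/30) = 0.122, so ±1.96 × 0.122 = ±24 points. It is also ±24 at 70% vs 59%.
- 6-month difference at 45% vs 25%: SE = √(0.45 × 0.55/30 + 0.25 × 0.75/30) = 0.120, so ±24 points.
- 6-9 month HR if truly 1.0: expected events are 30 × 0.25 = 7.5 (control) and 30 × (0.591 - 0.25) = 10.2 (intervention). SE of log HR ≈ √(1/7.5 + 1/10.2) = 0.48, and exp(1.96 × 0.48) ≈ 2.6, so the 95% CI is about 0.39 to 2.57.

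**The case against.** The case for leaving the plan alone has real substance.

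- **An overall HR of 0.68 is not false if the effect merely stops.** Relapse at 9 months is still 59% against 70%, a cumulative benefit of 11 points. This stands. A reader might infer that the plan would report a benefit that does not exist; in this case it would not. What the HR leaves open is whether the effect continues.
- **Full catch-up needs active reversal.** It takes a relapse hazard about 51% higher on intervention after month 6, and nothing in the documents suggests this; the conceptual model argues for persistence. A significantly protective HR would then be uncommon (7.5% at a 6-9 month HR of 1.5). This stands as a limit on how likely the extreme case is.
- **The planning rates do not point to waning.** They give HRs of 0.48 for months 0-6 and ln(0.61/0.75)/ln(0.30/0.55) = 0.34 for months 6-9. It is tempting to cite these as evidence of a changing effect, but they are a by-product of applying one 45% reduction to cumulative risk at both times, and they imply strengthening. They are not used here as evidence.
- **The curves already contain relapse at 6 and 9 months.** Correct. It would be too strong to say that these quantities are never estimated. Only the prespecified difference with its confidence interval is missing.
- **A 6-9 month HR is a weak basis for a conclusion.** Also correct. It compares only women still abstinent at 6 months, so it is no longer a fully randomised contrast, and it is very imprecise.
- **This is a 60-woman pilot.** That limits the weight of the point, but does not remove the mismatch between a stated purpose and the estimate offered for it.

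**Conclusion.** The concern holds as a mismatch between purpose and estimate. The follow-up after month 6 exists to assess sustainability, and the one numerical estimate planned cannot separate a lasting effect from one that stops (overall HR about 0.68) or fully reverses by 9 months (about 0.85). The masking has a limit: beyond a 6-9 month HR of about 2, the overall HR exceeds 1.

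These sizes rest on the plan's 6-month rates and its 9-month control rate, on a 0-9 month horizon that the plan does not state, and on later HRs that are assumptions. The documents do not support a claim that the effect will wane, nor that the Cox analysis is invalid. The addition is a cheap improvement and leaves the primary analysis unchanged.

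**What to change.** In section 3.1.12:

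1. Keep the Cox HR as the primary estimate and state its time horizon.
2. Add the between-arm Kaplan-Meier difference in cumulative relapse at 6 and at 9 months, each with a 95% CI.
3. State that any conclusion on sustainability will rest on the 9-month difference read alongside the 6-month difference, and not on the overall HR.
4. Report HRs for months 0-6 and 6-9 as descriptive only, noting that the later one is restricted to women still abstinent at 6 months.

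The cost is SAP wording and a little analysis; the daily calendars and the M6 and M9 visits already supply the data. The downside is imprecision: about ±24 points on each difference, and a factor of about 2.6 either way on the 6-9 month HR if its true value is 1.0. In the simulations, power to detect a change in HR at 6 months was about 18% if the effect stops and 40% at a later HR of 1.5. The additions should therefore be presented as estimates with intervals and not as tests, and the pilot may be unable to settle the question.
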